 - k. Biochemistry, hematology, coagulation, LFTs, and urinalysis parameters are described in Section 7.5.6. Clinical laboratory tests will be analyzed by a central laboratory. Within 4 days prior to dosing, LFT measurements will be analyzed by a local laboratory and confirmed by a central laboratory. Local clinical laboratory results for LFT measurements must be available and reviewed by the Investigator before study drug administration.
 - l. During Screening and throughout the Dosing Period, abnormal results for troponin I tests should be repeated. During the Dosing Period only, local clinical laboratory results must be drawn within 4 days prior to dosing and available and reviewed by the Investigator before study drug administration. Troponin I levels will be measured on the first day of the Safety and PD Follow-up Period (Day 197), and thereafter, approximately every 168 days for the duration of the study. Troponin I results from Day -1, Day 85, Day 113, Day 197, and for the remainder of the study will be analyzed by a central laboratory. Central laboratory results are not required before study drug administration.
 - m. Drugs of abuse are described in Section 7.5.6.3. Screening for drugs of abuse will be performed for patients who are above the age of legal consent.
 - n. Randomization occurs between Day -1 and Day 1.
 - o. Study drug will be administered via SC injection as described in Section 6.2.2.

-
- p. Blood and urine samples for PK analysis will be collected at the time points listed in [Table 12](#).
 - q. On Day 1, the blood sample for PD analysis must be collected within 2 hours predose. The remaining PD samples should be collected at approximately the same time of day corresponding to the predose collection (± 1 hour), as applicable.
 - r. During the screening period, 24-hour urine collections will be completed at 2 separate time points. The first screening 24-hour (± 30 minutes) urine collection will be used to assess eligibility. The second screening 18-24-hour urine collection will only be initiated after eligibility is confirmed.
 - s. Single, 18-24-hour urine sample collections will be performed. The 24-hour urine collection starting on Day -1 must conclude on Day 1 before administration of the first dose of study drug. The 24-hour urine collection should be completed within 4 days prior to the study visit for Day 29, Day 57, Day 85, Day 113, Day 141, and Day 169, and the Q28D Safety and PD Follow-up visits.

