Full physical examination ^f	X								X	
Symptom-directed physical examination ^f		X	X	X	X	X	X	X		X
Height	X									
Body weight and BMI ^g	X	X							X	X
Vital signs ^h	X	X	X	X	X	X	X	X	X	X
12-lead ECG ⁱ	X	X	X	X			X		X	X
Pregnancy test/FSH screening ^j	X	X					X		X	X
Clinical laboratory assessments ^k	X	X	X	X	X	X	X	X	X	X
Urine sample for drugs of abuse ^l	X	X								
Randomization			X							
Study drug administration ^m			X							
Blood and urine samples for PK analyses ⁿ			X	X						
Blood samples for PD analyses ^o	X		X		X	X	X	X	X	X
Blood and urine samples for exploratory ██████████			X		X		X		X	
Blood sample for ADA analysis			X				X		X	

Table 1: Schedule of Assessments for Single-ascending Dose Cohorts in Healthy Subjects (Part A)

Study Stage	Screening	Dosing Period			Postdose Follow-up Period					Safety and PD Follow-up ^a
Study Day	Days -45 to -2	Day -1 ^b	Day 1	Day 2 ^c	Day 8	Day 15	Day 29	Day 43	Day 57/EOT ^d	Q28D
Visit Window (days)						(±2)	(±3)	(±3)	(±3)	(-2 to +5)
Review/record AEs ^p			X							
Prior and concomitant medications	X									

Abbreviations: ADA=antidrug antibodies; AE=adverse event;; BMI=body mass index; D=Day; ECG=electrocardiogram; EOT=end of treatment; FSH=follicle-stimulating hormone; ICF=informed consent form; LFT=liver function tests; PD=pharmacodynamics; PK=pharmacokinetic; Q=every; SC=subcutaneous.

Notes:

- When scheduled at the same time points, the assessments of vital signs and 12-lead ECGs must be performed first, before the physical examinations, blood sample collections, and urine collections.
- Assessments should be performed predose, where applicable, and unless otherwise noted.

^a Safety and PD follow-up will continue: 1) for at least 57 days, and 2) until plasma glycolate decreases to a level that is no more than 20% above of baseline or until plasma glycolate is below the upper limit of normal (≤ 14 nmol/mL).

^b Subjects will be admitted to the clinical study center for predose assessments.

^c Subjects will be discharged from the clinical study center following the completion of the assessments.

^d If a subject chooses to withdraw consent, every effort should be made to conduct the assessments performed at the EOT visit.

^e Complete medical history will be obtained at screening and any changes will be updated on admission to the clinical study center. Events occurring after signing of the ICF and before study drug administration will be captured as medical history.

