 - v. Blood samples for exploratory [REDACTED] are optional for pediatric patients who exceed the maximum blood volume collection limits listed in [Table 13](#).
 - w. Blood sample for pyridoxine (vitamin B6) is required only for patients receiving therapeutic pyridoxine. On days when a blood sample for pyridoxine will be collected, patients should be instructed not to take vitamin B6 before the blood sample is collected and study drug is administered.
 - x. During the Safety and PD follow-up period, blood sample for ADA should be collected every 56 days after Day 141 (eg, Day 197, Day 253, Day 309) for the duration of the study.
 - y. AEs occurring after signing of the ICF and before study drug administration will be captured as medical history, while all AEs that occur after study drug administration, and baseline AEs that worsen after study drug administration, must be recorded and reported as AEs.

Table 3: Schedule of Assessments for Multiple-ascending Dose Cohorts in Patients with Primary Hyperoxaluria Type 1 (Part B) who Previously Received Placebo and will Receive Open-Label ALN-GO1 – Monthly Dosing

Study Stage	Dosing Period												Postdose Follow-up Period ^a						Safety and PD Follow-up	
Study Day (D)	84	85	86	87	99	112	113	127	140	141/EOT ^b	142	143	168	169	196	197	224	225	253; then, Q28D	
Visit Window (D)					±2		±4	±4		±4				±4		±4		±4		±4
Full physical examination ^c																		X		
Symptom-directed physical examination ^c		X	X		X		X	X		X				X		X				X
Height ^d		X								X				X				X	X	
Body weight and BMI		X ^e								X				X				X	X	
Vital signs ^f		X	X		X		X	X		X				X		X		X	X	
12-lead ECG ^g		X	X				X			X				X		X		X	X	
Echo		X												X					X ^h	
Pregnancy test ⁱ		X					X			X				X		X		X	X	
Clinical laboratory assessments ^j		X	X		X		X	X		X				X		X		X	X	
Troponin I ^k		X					X			X				X					X	
Study drug administration ^l		X					X			X										
Blood and urine samples for PK analyses ^m		X	X	X	X		X			X	X	X		X						
Blood sample for PD analyses ⁿ		X			X		X	X		X				X		X		X	X	
24-hour urine collection for PD analyses ^o	X					X			X				X		X		X		X	
██████████ PD analysis ^p		X	X		X		X	X		X				X		X		X	X	

Table 3: Schedule of Assessments for Multiple-ascending Dose Cohorts in Patients with Primary Hyperoxaluria Type 1 (Part B) who Previously Received Placebo and will Receive Open-Label ALN-GO1 – Monthly Dosing

Study Stage	Dosing Period												Postdose Follow-up Period ^a						Safety and PD Follow-up

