7.5.7.2. Eliciting and Recording Adverse Events

Eliciting Adverse Events

The patient should be asked about medically relevant changes in his/her health since the last visit. The patient should also be asked if he/she has been hospitalized, had any accidents, used any new medications, or changed concomitant medication routines (both prescription and OTC). In addition to patient observations, AEs will be documented from any clinically relevant laboratory findings, physical examination findings, ECG changes, or other findings that are relevant to patient safety.

Recording Adverse Events

The Investigator is responsible for recording non-serious AEs that are observed or reported by the patient after administration of the first dose of study drug regardless of their relationship to study drug through the end of study. Non-serious AEs will be followed until the end of study.

The Investigator is responsible for recording SAEs that are observed or reported by the patient after the time when the informed consent is signed regardless of their relationship to study drug through the end of study. SAEs will be followed until satisfactory resolution, until baseline level is reached, or until the SAE is considered by the Investigator to be chronic or the patient is stable, as appropriate.

All AEs must be recorded in the source records for the clinical study center and in the eCRF for the patient, whether or not they are considered to be drug-related. Each AE must be described in detail: onset time and date, description of event, severity, relationship to investigational drug, action taken, and outcome (including time and date of resolution, if applicable).

For purposes of this study, ISRs are considered to be Adverse Events of Clinical Interest. These AEs will be recorded both on a supplemental eCRF and on an Adverse Event of Clinical Interest form. Refer to the eCRF completion guidelines for details on these forms.

For SAEs, record the event(s) in the eCRF. If the EDC system is unavailable, complete the back-up SAE form.

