7.5.7.3. Serious Adverse Events Require Immediate Reporting to Sponsor/Designee

An assessment of the seriousness of each AE will be made by the Investigator. Any AE and laboratory abnormality that meets the SAE criteria in Section 7.5.7.1 must be reported to the Sponsor or designee within 24 hours from the time that clinical study center staff first learns of the event. All SAEs must be reported regardless of the relationship to study drug.

The initial report should include at least the following information:

- Subject/Patient's study number
- Description and date of onset of the event
- Criterion for serious
- Preliminary assignment of relationship to study drug, and
- Investigator/site information

To report the SAE, complete the eCRF. If the EDC system is unavailable, complete the back-up SAE form. Within 24 hours of receipt of follow-up information, the Investigator must update the SAE form. SAEs must be reported using the contact information provided in the Study Reference Guide.

Appropriate remedial measures should be taken by the Investigator using his/her best medical judgment to treat the SAE. These measures and the patient's response to these measures should be recorded. All SAEs, regardless of relationship to study drug, will be followed by the Investigator until satisfactory resolution or the Investigator deems the SAE to be chronic or stable. Clinical, laboratory, and diagnostic measures should be employed by the Investigator as needed to adequately determine the etiology of the event.

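### Six schedule footnotes send events between consent and first dose to medical history with no exception for serious ones, while Protocol 7.5.7.2 and SAP 6.1.1 require SAEs to be recorded from consent

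*Protocol*

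**What the plan says.** **Schedules.** Table 1 footnote p, Table 2 footnotes c and y, and Table 4 footnotes c and y carry the same instruction: "AEs occurring after signing of the ICF and before study drug administration will be captured as medical history". Table 1 footnote e is wider: "Events occurring after signing of the ICF and before study drug administration will be captured as medical history". Footnotes p and y then set these events against AEs that arise after dosing and "baseline AEs that worsen after study drug administration, must be recorded and reported as AEs". None of the six mentions seriousness or refers to Section 7.5.7.

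**Safety section.** Protocol 7.5.7.2 uses two start points. Under the first, the investigator's duty covers "recording non-serious AEs that are observed or reported by the patient after administration of the first dose of study drug". The second is earlier: "The Investigator is responsible for recording SAEs that are observed or reported by the patient after the time when the informed consent is signed". The same section adds: "For SAEs, record the event(s) in the eCRF". Protocol 7.5.7.3 says that an event meeting the SAE criteria "must be reported to the Sponsor or designee within 24 hours from the time that clinical study center staff first learns of the event", and "All SAEs must be reported regardless of the relationship to study drug".

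**SAP.** Section 6.1.1 repeats both start points. It does not restate the 24-hour limit, which rests on Protocol 7.5.7.3.

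**The concern.** The footnotes agree with Section 7.5.7.2 for non-serious AEs and conflict with it for SAEs. Site staff work visit by visit from the schedule of assessments, so the footnotes are operative instructions. Take a patient who is hospitalised after consent and before Day 1. The schedule asks for a medical-history entry; Section 7.5.7 asks for an SAE record and a report within 24 hours.

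At stake are the completeness and timeliness of SAE reporting during screening, and the completeness of the SAE listings. Serious events in screening are plausible. Protocol 1.1 describes recurrent stone disease in PH1. Table 9 (area E) treats an unplanned or extended inpatient stay for a suspected adverse event as an SAE, with no statement that this begins only at dosing.

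**Working it through.** The check is textual; there is no plan figure to reproduce.

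**1. Start points side by side**

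| Source | Non-serious AE before first dose | SAE before first dose |
|---|---|---|
| Table 1 e, p; Table 2 c, y; Table 4 c, y | medical history | medical history (no exception stated) |
| Protocol 7.5.7.2 | not recorded as an AE | recorded as an SAE from consent |
| Protocol 7.5.7.3 | no 24-hour report | reported within 24 hours |
| SAP 6.1.1 | not recorded as an AE | recorded as an SAE from consent |

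The first column is consistent. The second is not. Table 3 has no such footnote, and needs none, because it covers only patients who have already received placebo.

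**2. Can the footnotes be read as covering only non-serious events?** Not from their words. Protocol 7.5 treats SAEs as a subset of AEs, and Section 7.5.7.2 adds the qualifier when it means non-serious events. The footnotes do not.

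**3. Possible delay.** The history footnotes provide for an update on Day -1 (Part B) or on admission, which is also Day -1 (Part A). If a site waited for that update, an event on Day -45 would be entered 45 − 1 = 44 days later, against a limit of 24 hours. This is the longest case under that assumption, not an expected delay.

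**4. What a history entry lacks.** SAP 7.3.4 codes history by system organ class and preferred term, and names no seriousness field. The AE listing in SAP 7.4.1 carries an SAE flag. The history listing covers randomized subjects only, so it would not show an event in someone who consented and was then not randomized.

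**5. Effect on the analyses.**
- SAP 4.2.1 restricts the Safety Analysis Set to those dosed.
- For Part B, SAP 7.4.1 counts AEs with onset on or after first dose.
- In both parts, the SAE rows of the overview and the SAE tables are treatment-emergent.
- For Part A, SAP 7.4.1 does not spell out an onset rule. I assume counting from first dose, in line with the treatment-emergent tabulations in Protocol 8.2.7.
- The SAE listings in Protocol 8.2.7 and SAP 7.4.1 are not restricted to treatment-emergent events, so a pre-dose SAE could be missing from them.

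**6. Extent.** Planned enrolment is 40 + 24 = 64 (Protocol 4.3). The window is up to 45 days in Part B (Protocol 4.2) and Day -45 to dosing on Day 1 in Part A (Protocol 4.1.1). Part A has one centre and Part B about 12 (Protocol 4.1), so differences between sites can concern at most the 24 planned Part B patients. People who consent but are not enrolled are also exposed; the documents give no number for them.

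**The case against.** The best defence is that the rule is stated plainly where one would look for it. Section 7.5.7.2 separates the two start points, and Section 7.5.7.3 admits no exception. The footnotes annotate the rows for history and AE review, match Section 7.5.7.2 for ordinary AEs, and do not bar an SAE report. A history entry and an SAE form can coexist. Protocol 7.5.7.2 and 7.5.7.3 also send sites to eCRF completion guidelines and a Study Reference Guide, which are not available here and may settle the matter.

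Much of this stands. The gap is a missing qualifier, and how often a site would be misled cannot be estimated. What does not fall is that the footnotes are unqualified and no passage gives either text precedence.

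The safety consequence is also limited:
- The stopping rules in Table 6 and the rows of Table 8 turn on events related to study drug, which a pre-dose event cannot be. Table 7 also covers disease-related events, but its action is to discontinue dosing, which has not begun.
- The expedited routes in Section 7.5.7.4 for suspected reactions do not apply. The route for events connected with study conduct might.
- The event need not be lost to the investigator, who updates the history before dosing. Exclusion criterion 5 covers significant illness in the 7 days before first dose, other than PH1 in Part B.

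**Conclusion.** The concern holds as an internal inconsistency in safety reporting. It is not a questionable design choice: the intended rule, SAEs from consent, is clear in Protocol 7.5.7.2 and SAP 6.1.1. A screening-period SAE could be entered only as medical history, and so be missed or delayed in SAE reporting and absent from the SAE listings. This rests on a site following the schedule literally, without turning to Section 7.5.7.

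A reader might infer more, and the documents do not support it:
- *That no pre-dose SAE would be reported.* The footnotes do not forbid reporting, and a site that follows Section 7.5.7 will report.
- *That handling could differ between sites across the whole study.* Part A is single-centre, so this is possible only in Part B.
- *That the primary endpoint or the drug-related stopping rules are compromised.* Primary AE incidence and the treatment-emergent summaries should not change, given the counting from first dose described above (explicit for Part B, assumed for Part A), and the stopping rules are essentially unaffected.

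**What to change.** Reconcile the passages. In Table 1 footnotes e and p, Table 2 footnotes c and y, and Table 4 footnotes c and y, limit the medical-history instruction to non-serious AEs. In footnote e this also means replacing the word *Events*. Add to each: *SAEs from signing of the ICF are recorded and reported per Sections 7.5.7.2 and 7.5.7.3.* Check that the eCRF completion guidelines and the Study Reference Guide say the same.

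The cost is a few words in six footnotes and a short note to sites. It adds no reporting burden beyond what Section 7.5.7 already requires, and SAP 6.1.1 needs no change.

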 - f. Vital signs (blood pressure, pulse rate, body temperature, and respiration rate) will be measured in the supine position after the patient has rested comfortably for 10 minutes. On Day 85 only, vital signs will be measured within 2 hours predose; and 30 (±5 minutes) and 4 hours (±15 minutes) postdose.

- g. All 12-lead ECGs are triplicate, using centralized equipment. ECGs will be measured approximately 5 minutes apart. Recordings will be obtained after the patient has rested comfortably in the supine position for approximately 10 minutes. Patients should remain supine between ECGs. On dosing days, ECGs will be measured within 2 hours predose; and at 1 hour (± 20 minutes), 2 hours (± 20 minutes), and 4 hours (± 20 minutes) postdose. On all other days, ECGs should be collected at approximately the same time of day corresponding to the predose collection (± 1 hour).
- h. Echo will be performed during the first visit of the Safety and PD Follow-up Period (Day 253), and thereafter, approximately every 168 days corresponding with visits to the clinical study center for the duration of the study.
- i. Pregnancy tests will be performed for women of childbearing potential only. A serum pregnancy test will be performed after the onset of menarche if the patient was not of childbearing potential at screening, and a serum or urine pregnancy test will be performed per the Schedule of Assessments and any time pregnancy is suspected. The results of the pregnancy test must be known before ALN-GO1 administration.
- j. Biochemistry, hematology, coagulation, LFTs, and urinalysis parameters are described in Section 7.5.6. Clinical laboratory tests will be analyzed by a central laboratory. Within 4 days prior to dosing, LFT measurements will be analyzed by a local laboratory and confirmed by a central laboratory. Local clinical laboratory results for LFT measurements must be available and reviewed by the Investigator before study drug administration.

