██████████ PD analysis ^t		X	X	X		X		X	X		X		X		X		X	X		X		X		X		X
Blood and urine samples ██████████ ██████████ ██████████			X					X		X			X ^v					X			X					
Blood sample for pyridoxine (vitamin B6) levels ^v			X					X		X			X					X			X			X		X
Blood samples for ADA analysis			X					X		X			X					X			X			X		X ^x
Review/record AEs ^y			X																							
Concomitant medications			X																							

Abbreviations: ADA=antidrug antibodies; AE=adverse event; BMI=body mass index; D=day; ECG=electrocardiogram; Echo=echocardiography; eGFR=estimated glomerular filtration rate; EOT=end of treatment; FSH=follicle-stimulating hormone; ICF=informed consent form; LFT=liver function test; PD=pharmacodynamics; PK=pharmacokinetic; Q=every; SC=subcutaneous.

Notes:

- When scheduled at the same time points, the assessments of vital signs and 12-lead ECGs must be performed first, before the physical examinations, blood sample collections, and urine collections.
- Assessments should be performed predose, where applicable, unless otherwise noted.
- Grey columns indicate the study day when the 24-hour urine collection for PD analysis should begin. Patients may be admitted to the clinical study center to complete the 24-hour urine collections.
 - a. Patients will be invited to participate in an open-label extension study once they complete the postdose follow-up period on Study Day 169. For patients who do not enroll in the open-label extension study, safety and PD follow up will continue until plasma glycolate is <20% above baseline or ≤ the ULN AND 24-hour urinary oxalate is >80% of baseline, or until the SRC makes a decision per investigator request to discontinue follow-up on a case-by-case basis. The decision cannot be made until after completion of the postdose follow-up period (84 days after last dose).
 - b. Patients initially randomized to placebo will receive open-label ALN-GO1.
 - c. Complete medical history (including documentation or confirmation of PH1) will be obtained at screening and any changes will be updated on Day -1. AEs occurring after signing of the ICF and before study drug administration will be captured as medical history.
 - d. See Section 7.5.3 for assessments to be performed during a full physical examination or symptom-directed physical examination.

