 - e. During screening and at EOT, height will be measured for all patients; thereafter, height will only be measured for patients <18 years of age. Additionally, for patients <18 years of age, at each time point, height will be measured in centimeters, and in triplicate, to facilitate calculation of eGFR using the Schwartz Bedside Formula.
 - f. Day -1 body weight will be used for calculation of the ALN-GO1 or placebo (study drug) dose to be administered during the dosing period.
 - g. Vital signs (blood pressure, pulse rate, body temperature, and respiration rate) will be measured in the supine position after the patient has rested comfortably for 10 minutes. On Day 1 only, vital signs will be measured within 2 hours predose; and 30 (±5 minutes) and 4 hours (±15 minutes) postdose.
 - h. All 12-lead ECGs are triplicate, using centralized equipment. ECGs will be measured approximately 5 minutes apart. Recordings will be obtained after the patient has rested comfortably in the supine position for approximately 10 minutes. Patients should remain supine between ECGs. On dosing days, ECGs will be measured within 2 hours predose; and at 1 hour (±20 minutes), 2 hours (±20 minutes), and 4 hours (±20 minutes) postdose. On all other days, ECGs should be collected at approximately the same time of day corresponding to the predose collection (±1 hour).
 - i. Echo will be performed during the first visit of the Safety and PD Follow-up Period (Day 197) and approximately every 168 days corresponding with visits to the clinical study center for the duration of the study.
 - j. Pregnancy tests will be performed for women of childbearing potential only. A serum pregnancy test will be performed at Screening or after the onset of menarche if the patient was not of childbearing potential at screening, and urine pregnancy tests will be performed thereafter per the Schedule of Assessments and any time pregnancy is suspected. The results of the pregnancy test must be known before study drug administration. FSH will be measured at Screening only to confirm post-menopausal status.

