4.5. Blinding

This is a single-blind, placebo-controlled study; therefore, only the study subjects/patients will be blinded to treatment assignment. Patients in Part B dosed monthly will be unblinded on or after Day 78 in order for patients and their families to be better prepared for the transition to receive ALN-GO1 if initially randomized to placebo. Patients dosed quarterly will be unblinded to initial treatment assignment following completion of the postdose follow-up period. The Investigators, Medical Monitors at the Sponsor and CRO, clinical study center personnel, pharmacokineticist, and members of the SRC will have knowledge of the treatment assignment. The clinical study center pharmacy staff will maintain the single-blind according to clinical study center-specific procedures and the Pharmacy Manual. Syringes containing dispensed study drug will be masked in the pharmacy before transfer to the clinic.

During the blinded period, if the subject/patient becomes seriously ill during the study, and the treating physician determines that the clinical management of the subject requires that the subject know the study drug assignment, the Investigator may break the blind, as necessary. If time permits, clinical study center personnel should contact the Medical Monitor before unblinding to discuss the need to unblind the subject/patient. A record of when the blind was broken, who broke the blind, and why it was broken, will be maintained in the Trial Master File.

See the Pharmacy Manual for additional details.

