4.7.2. Study Drug Dosing, Study Progression, and Dose Escalation in Part B

Preliminary safety and PD data from Part A was evaluated by the SRC. The initial dose level of 1.0 mg/kg for administration in Part B was shown to be well-tolerated, and the lowest pharmacologically active dose. In Part B, all patients in a cohort dosed monthly will receive the same dose for each of the 3 study drug doses. Patients initially receiving 3 doses of placebo will receive 3 doses of ALN-GO1, with all 3 doses being the same for each of the 3 administrations of ALN-GO1. Patients in a cohort dosed quarterly who are randomized to ALN-GO1 will receive the same dose for each of the 2 study drug doses. Patients initially receiving 1 dose of placebo on Day 1 will receive 1 dose of ALN-GO1 on study Day 85. The maximum dose administered will not exceed 6.0 mg/kg.

Dose levels and/or dosing regimen in each cohort in Part B may be modified by the SRC. The next higher dose cohort can be enrolled after at least 3 patients in the previous cohort receive their first and second dose and have been followed for at least 14 days following the second dose of study drug. The SRC must review accumulating safety data from both single- and multiple-ascending dose cohorts to confirm the dose level and permit dosing in the next MAD cohort. In

Part B, patients randomized to placebo will be administered active ALN-GO1 in an open-label manner according to the same dose and assessment schedule for the cohort to which they were initially assigned.

Based on SRC review of accumulated safety, tolerability, and PD data, 3 additional cohorts may be enrolled and dosed according to the same eligibility criteria in Part B to better define safety or PD effects. Additional cohorts may be enrolled at higher, lower, or intermediate dose levels, but will not exceed the maximum administered dose of 6.0 mg/kg, and will follow the protocol-specified dose escalation criteria.

Based on SRC review of accumulated safety, tolerability, and available PD data, up to 2 cohorts in Part B may be extended by up to 4 additional patients per cohort based on study progression and stopping rules. These patients will all receive active drug, not placebo.

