6.2.1. Description

ALN-GO1 Solution for Injection (SC use) is a clear, colorless to pale yellow solution essentially free of particulates. ALN-GO1 will be supplied by the Sponsor as a sterile solution for SC injection at a targeted concentration of 200 mg/mL. Placebo will be supplied by the clinical study center as a sterile, preservative-free normal saline 0.9% solution for SC injection.

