Study Day	Protocol Time (hh:mm)	Blood PK	Urine PK	Pooled Urine
	08:01 (±15 min)			X (08:01-12:00)
	12:00 (±15 min)	X		
	12:01 (±15 min)			X (12:01-24:00)
Day 142 ^b	24:00 (±30 min)	X		
Day 143 ^b	48:00 (±30 min)	X		
Day 169 ^b	Anytime during visit	X		

a. For subjects initially randomized to ALN-GO1

b. Collect blood and urine samples from patients who previously received placebo and continue on-study to receive open-label ALN-GO1.

Table 12 contains a detailed schedule for the collection of blood and urine samples for PK analysis for patients dosed quarterly in Part B.

Table 12: Pharmacokinetic Time Points for Patients with PH1 (Part B – Quarterly Dosing)

Study Day	Protocol Time (hh:mm)	Blood PK	Urine PK	Pooled Urine
Day 1	Predose (within 2 hours of dosing)	X	X	
	00:00 (dose)			X (00:00-04:00)
	00:30 (±2 min)	X		
	02:00 (±5 min)	X		
	04:00 (±10 min)	X		X (04:01-08:00)
	04:01 (±10 min)			
	06:00 (±15 min)	X		
	08:00 (±15 min)	X		X (08:01-12:00)
	08:01 (±15 min)			
	12:00 (±15 min)	X		X (12:01-24:00)
	12:01 (±15 min)			
Day 2	24:00 (±30 min)	X		
Day 3	48:00 (±30 min)	X		
Day 15	Anytime during visit	X		
Day 85	Predose (within 2 hours of dosing)	X	X	
	00:00 (dose)			X (00:00-04:00)
	00:30 (±2 min)	X		
	02:00 (±5 min)	X		
	04:00 (±10 min)	X		X (04:01-08:00)
	04:01 (±10 min)			
	06:00 (±15 min)	X		
	08:00 (±15 min)	X		X (08:01-12:00)
	08:01 (±15 min)			
	12:00 (±15 min)	X		X (12:01-24:00)
	12:01 (±15 min)			
Day 86	24:00 (±30 min)	X		
Day 87	48:00 (±30 min)	X		

Table 12: Pharmacokinetic Time Points for Patients with PH1 (Part B – Quarterly Dosing)

Study Day	Protocol Time (hh:mm)	Blood PK	Urine PK	Pooled Urine
Day 99	Anytime during visit	X		
Day 113	Anytime during visit	X		

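### Quarterly placebo patients have timed post-dose vital signs after saline on Day 1 but not after their only ALN-GO1 dose on Day 85

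*Protocol*

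**What the plan says.** Table 4 schedules study drug on Day 1 and Day 85, and its vital-signs row is marked on both days and again on Day 86. Footnote g to that row restricts the timed readings: "On Day 1 only, vital signs will be measured within 2 hours predose; and 30 (±5 minutes") and 4 hours after the dose. For anything not given a specific time, the general note under the table applies: "Assessments should be performed predose, where applicable, unless otherwise noted".

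Section 4.7.2 describes the treatment of quarterly patients who start on placebo: "Patients initially receiving 1 dose of placebo on Day 1 will receive 1 dose of ALN-GO1 on study Day 85". Their Day 1 injection is saline (Section 6.2.1).

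Monthly placebo patients move to their own schedule, Table 3, when they cross over. Its footnote f moves the same timed readings to the first active dose: "On Day 85 only, vital signs will be measured within 2 hours predose", again with 30-minute and 4-hour sets. Section 7.5.1 and SAP Section 6.1.2 describe how vital signs are taken and which are recorded, but add no post-dose times.

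**The concern.** The primary objective is safety and tolerability, and Section 3.1 names vital signs among the safety measures that accompany adverse event incidence. Section 1.3 supports the delayed-start design partly because patients moving from placebo to active drug add safety data. For one group, the quarterly patients who start on placebo, the schedule places the acute readings after the wrong injection.

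What is lost is scheduled blood pressure, temperature and respiratory rate in the first hours after first exposure, in a population that may be as young as 6 years (Section 5.1.1). A symptomatic reaction would be reported as an adverse event, and the ECGs give ventricular rate. An asymptomatic change in the other three measures would not be looked for on schedule. A patient with readings after placebo but not after ALN-GO1 also cannot serve as his or her own control for acute vital signs.

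The omission looks unintended. Footnote g in Table 4 reads like footnote g in Table 2, where Day 1 is the only first dose. Table 4, however, covers both quarterly arms through Day 85. That it was carried over without adaptation is an inference; no reason for limiting the readings to Day 1 is given.

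**Working it through.** The plan gives no figure on this point, so the check compares the schedules and counts.

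**Timed sets (30 minutes and 4 hours) after the first ALN-GO1 dose, by group**

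| Group | Source | First ALN-GO1 dose | Timed sets | First scheduled post-dose blood pressure |
|---|---|---|---|---|
| Part A, ALN-GO1 | Table 1, footnote h | Day 1 | 2 of 2 | 0.5 h |
| Monthly, ALN-GO1 | Table 2, footnote g | Day 1 | 2 of 2 | 0.5 h |
| Monthly, placebo then ALN-GO1 | Table 3, footnote f | Day 85 | 2 of 2 | 0.5 h |
| Quarterly, ALN-GO1 | Table 4, footnote g | Day 1 | 2 of 2 | 0.5 h |
| Quarterly, placebo then ALN-GO1 | Table 4, footnote g and general note | Day 85 | 0 of 2 | about 24 h (Day 86) |

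Quarterly patients randomized to ALN-GO1 also have no timed sets after their second dose on Day 85, but they had them after the first. The tables' evident principle is to take timed readings at the first dose of a course. Only the last row departs from it for active drug.

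**Other monitoring on Day 85.** Table 4 footnote h asks for ECGs on dosing days, at 1, 2 and 4 hours post-dose. Table 12 (Appendix 11.1) has blood draws for pharmacokinetics at 0.5, 2, 4, 6, 8 and 12 hours. Day 85 is thus already an intensively attended dosing day.

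**Number affected**

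- Section 4.1.2: 4 patients per cohort, randomized 3:1, gives 4 × 1/4 = 1 placebo patient, or 25% of an unexpanded quarterly cohort. Expansion patients all start on ALN-GO1, so with 4 added the fraction is 1 of 8 (12.5%).
- The number of quarterly cohorts is not fixed. Section 4.1.2 allows 2 + 3 = 5 cohorts, and Section 1.4 sets the first at every 28 days. That leaves 0 to 4 quarterly cohorts, so 0 to 4 patients. The synopsis allows up to 6 cohorts; if all were randomized and all but the first quarterly, the upper end would be 5.
- SAP Section 7.2.3 lays out two quarterly dose levels with one placebo-first patient each: 2 × 1 = 2.

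**The case against.** The wording of the footnote is not in dispute; the case against concerns its consequence.

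- **Few patients, perhaps none.** The SAP table is a display layout, not an enrolment plan, and quarterly cohorts need not be opened. This stands, and the size is therefore given as a range.
- **No planned analysis depends on the missing readings.** The SAP is descriptive and plans no within-patient comparison of acute vital signs. The by-visit layout in SAP Section 7.2.3 has no within-day rows, so 30-minute and 4-hour values would appear mainly in listings. This also stands. The loss is of scheduled safety observation, plus at most one patient's values at two time points per dose level. SAP Section 7.2.2 does realign crossover safety data to the first ALN-GO1 dose, and Section 7.4.4 summarises vital signs regardless of treatment sequence, so those values would have had a place.
- **Acute risk is low.** The risks listed in Section 1.5 are not acute haemodynamic, thermal or respiratory ones. Part B doses may not exceed those found safe in Part A (Table 9), where the timed readings were taken. The three ALN-GO1 patients in the same cohort have the readings at their own first dose, and the Safety Review Committee reviews data at least every 3 months. These points limit the severity. They do not explain why monthly crossover patients get the readings and quarterly ones do not.
- **The added sets are not entirely free.** Vital signs need 10 minutes of supine rest and must precede blood sampling due at the same time, while the 0.5-hour draw has a window of ±2 minutes. This is correct, but the same sequence is already run on Day 1.

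**Conclusion.** The concern holds, as a minor point. On the current text, a quarterly patient randomized to placebo has both timed post-dose vital-sign sets after saline and neither after the only ALN-GO1 dose in this study. The first scheduled post-dose blood pressure comes on Day 86, about 24 hours after dosing, against 0.5 hours in every other group.

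The number affected is 1 per randomized quarterly cohort: 0 to 4 under Section 4.1.2, assuming the first cohort is monthly, and 2 under the SAP layout. The conclusion rests on reading the unqualified Day 85 entry as predose, as the Table 4 note directs. Unscheduled readings remain possible, and patients may receive further doses in the extension study. The adverse event endpoint and the planned comparisons are not affected.

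**What to change.** Amend Table 4 footnote g so that the predose, 30-minute and 4-hour vital signs apply on both Day 1 and Day 85, with the existing windows unchanged.

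Apply this to every patient on the quarterly schedule, not only to those who began on placebo. Section 4.5 states: "Patients dosed quarterly will be unblinded to initial treatment assignment following completion of the postdose follow-up period". Extra Day 85 readings confined to former placebo patients would reveal the initial assignment.

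The cost is two vital-sign sets per patient: 2 × 4 = 8 in a cohort of 4, or 2 × 8 = 16 in one expanded to 8. Both times match an existing Day 85 blood draw (0.5 and 4 hours), and the second also matches the 4-hour ECG. No visit or blood volume is added. Staff need only take vital signs before the draw, as they already do on Day 1.
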